3.2 Participant Exclusion Criteria

The participant must be excluded from participating in the trial if the participant has any of

the following:

- 3.2.1 Is currently participating and receiving study therapy or has participated in a study of an investigational agent and received study therapy or used an investigational device within 4 weeks of the first dose of treatment.
- 3.2.2 Has a diagnosis of immunodeficiency or is receiving systemic steroid therapy or any other form of immunosuppressive therapy within 7 days prior to the first dose of trial treatment.
- 3.2.3 Patients cannot have primary platinum refractory cancer, i.e. documented cancer progression while receiving platinum or within one month of receipt of a platinum based regimen.
- 3.2.4 Has received a prior anthracycline chemotherapy either for ovarian cancer treatment or another previous malignancy.
- 3.2.5 Left ventricular ejection fraction (LVEF) defined by multigated acquisition (MUGA) or echocardiogram which is below the institutional lower limit of normal prior to starting study treatment.
- 3.2.6 Has a known history of active TB (Bacillus Tuberculosis)
- 3.2.7 Known hypersensitivity to pembrolizumab or any of its excipients and/or liposomal doxorubicin.
- 3.2.8 Has had prior chemotherapy, targeted small molecule therapy, or radiation therapy within 2 weeks prior to study Day 1 or who has not recovered (i.e., \leq Grade 1 or at baseline) from adverse events due to a previously administered agent.
 - i. Note: If participant underwent major surgery, they must have recovered adequately from the toxicity and/or complications from the intervention prior to starting therapy.
 - ii. Note: Participants with alopecia are an exception to this criterion.
- 3.2.9 Has a known additional malignancy that is progressing or requires active treatment. In addition, patients cannot have been diagnosed with another malignancy within 3 years of starting treatment. Exceptions include fully resected basal cell carcinoma of the skin or squamous cell carcinoma of the skin, *in situ* cervical cancer, fully resected ductal carcinoma *in situ*, and stage IA, noninvasive grade I endometrial cancer, that has undergone curative therapy.
- 3.2.10 Has known active central nervous system (CNS) metastases and/or carcinomatous meningitis. Participants with previously treated brain metastases may participate provided they are stable (without evidence of progression by imaging for at least four weeks prior to the first dose of trial treatment and any neurologic symptoms have

returned to baseline), have no evidence of new or enlarging brain metastases, and are not using steroids for at least 7 days prior to trial treatment. This exception does not include clinically active and significant carcinomatous meningitis which is excluded regardless of clinical stability.

- 3.2.11 Has active autoimmune disease that has required systemic treatment in the past 2 years (i.e. with use of disease modifying agents, corticosteroids or immunosuppressive drugs). Replacement therapy (eg., thyroxine, insulin, or physiologic corticosteroid replacement therapy for adrenal or pituitary insufficiency, etc.) is not considered a form of systemic treatment.
- 3.2.12 Has known history of, or any evidence of active, non-infectious pneumonitis.
- 3.2.13 Has an active infection requiring systemic therapy.
- 3.2.14 Has a history or current evidence of any condition, therapy, or laboratory abnormality that might confound the results of the trial, interfere with the participant's participation for the full duration of the trial, or is not in the best interest of the participant to participate, in the opinion of the treating investigator.
- 3.2.15 Has known psychiatric or substance abuse disorders that would interfere with cooperation with the requirements of the trial.
- 3.2.16 Is pregnant or breastfeeding, or expecting to conceive within the projected duration of the trial, starting with the pre-screening or screening visit through 120 days after the last dose of trial treatment.
- 3.2.17 Has received prior therapy with an anti-PD-1, anti-PD-L1, or anti-PD-L2 agent.
- 3.2.18 Has a known history of Human Immunodeficiency Virus (HIV) (HIV 1/2 antibodies).
- 3.2.19 Has known active Hepatitis B (e.g., HBsAg reactive) or Hepatitis C (e.g., HCV RNA [qualitative] is detected).
- 3.2.20 Has received a live vaccine within 30 days of planned start of study therapy.
Note: Seasonal influenza vaccines for injection are generally inactivated flu vaccines and are allowed; however intranasal influenza vaccines (e.g., Flu-Mist®) are live attenuated vaccines, and are not allowed.
- 3.2.21 The following are additional exclusion criteria for patients enrolling post safety run in:
 - 3.2.21.1 Any clinical or radiographic evidence of a partial or complete bowel obstruction (small or large bowel) currently or within the past 6 months.
 - 3.2.21.2 No current dependency on total parental nutrition (TPN) or within the past 30 days.

3.3 Inclusion of Women and Minorities

Women of all races and ethnic groups are eligible for this trial.

4. REGISTRATION PROCEDURES

4.1 General Guidelines for DF/HCC and DF/PCC Institutions

Institutions will register eligible participants in the Clinical Trials Management System (CTMS) OnCore. Registrations must occur prior to the initiation of protocol therapy. Any participant not registered to the protocol before protocol therapy begins will be considered ineligible and registration will be denied.

An investigator will confirm eligibility criteria and a member of the study team will complete the ODQ protocol-specific eligibility checklist.

Following registration, participants may begin protocol therapy. Issues that would cause treatment delays should be discussed with the Overall Principal Investigator (PI). If a participant does not receive protocol therapy following registration, the participant's registration on the study must be canceled. Registration cancellations must be made in OnCore as soon as possible.

4.2 Registration Process for DF/HCC and DF/PCC Institutions

DF/HCC Standard Operating Procedure for Human Subject Research Titled *Subject Protocol Registration* (SOP #: REGIST-101) must be followed.

Exception: DF/PCC Affiliate sites must fax the entire signed consent form including HIPAA Privacy Authorization and the eligibility checklist to the Network Affiliate Office. The Network Affiliate Office will register the participant with the ODQ.

4.3 General Guidelines for Other Investigative Sites

Eligible participants will be entered on study centrally at the Dana-Farber Cancer Institute by the Project Manager. All sites should email or fax the documentation listed in section 4.4 to the Project Manager to verify treatment availability.

Following registration, participants should begin protocol therapy within 5 days. Issues that would cause treatment delays should be discussed with the Overall PI. If a participant does not receive protocol therapy following registration, the participant's registration on the study must be canceled. The Project Manager should be notified of cancellations as soon as possible.

4.4 Registration Process for Other Investigative Sites

To register a participant, the research nurse or study coordinator should email the following documentation to the Project Manager or fax to [contact]:

- Copy of clinic visit note documenting medical history and physical exam
- Lab documentation as per eligibility criteria
- Pathology report
- CT (chest/abdomen/pelvis) scan report
- ECHO/MUGA report
- EKG report
- Signed participant consent form, and consent process note
- HIPAA authorization form
- Completed Eligibility checklist

To complete the registration process, the Project Manager will

- follow the DF/HCC Standard Operating Procedure for Human Subject Research Titled *Subject Protocol Registration* (SOP #: REGIST-101) and register the participant on the protocol
- call and fax or email the research nurse or data manager at the participating site with the participant study number, and to confirm registration

NOTE: Registration can only be conducted during the business hours of 8:00 AM and 5:00 PM Eastern Time Monday through Friday. Same day treatment registrations will only be accepted with prior notice and discussion with the DF/HCC Lead Institution.

5. TREATMENT PLAN

5.1 Treatment Regimen

The treatment to be used in this trial is outlined below in Table 2:

Table 2 Trial Treatment

Drug*	Dose/Potency	Dose Frequency	Route of Administration	Regimen/Treatment Period	Use
Pegylated Liposomal Doxorubicin	40 mg/m ²	Once every 4 weeks	IV infusion over one hour per FDA package insert	One cycle = 28 days	FDA approved treatment for platinum resistant ovarian cancer
Pembrolizumab	200 mg as a flat dose	Once every 3 weeks	IV infusion per the FDA package insert	One cycle = 28 days	Experimental

*The drugs may be held independent of one another, however, the study clock will not stop as far as determining the cycle/day of treatment.

If there are 2 DLTs within the first 6 patients during the safety lead-in, the dose of PLD will be lowered to 30 mg/m².

5.2 Pre-Treatment Criteria

5.2.1 Cycle 1, Day 1

Participants must continue to meet all eligibility criteria prior to dosing on Cycle 1, Day 1, as outlined in Protocol Section 3.1.

5.2.2 Subsequent Cycles, on PLD treatment days: Patients must have all of the following:

Absolute Neutrophil Count: $\geq 1,500/\text{mcL}$
Hemoglobin: $\geq 9\text{g/dL}$
Platelets: $\geq 100,000/\text{mcL}$
Serum Creatinine $\leq 1.5 \times \text{ULN}$
Liver Function Test $\leq 2.5 \times \text{ULN}$
ECOG performance status of 0-1

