Absolute neutrophil count (ANC)	$\geq 1,500 / \mu\text{L}$
Platelets	$\geq 100,000 / \mu\text{L}$
Hemoglobin	$\geq 9 \text{ g/dL}$ or $\geq 5.6 \text{ mmol/L}$ without transfusion or EPO dependency (within 7 days of assessment)
Renal	
Serum creatinine OR Measured or calculated ^a creatinine clearance (GFR can also be used in place of creatinine or CrCl)	$\leq 1.5 \times$ upper limit of normal (ULN) OR $\geq 60 \text{ mL/min}$ for participant with creatinine levels $> 1.5 \times$ institutional ULN
Hepatic	
Serum total bilirubin	$\leq 1.5 \times$ ULN OR Direct bilirubin \leq ULN for participants with total bilirubin levels $> 1.5 \times$ ULN
AST (SGOT) and ALT (SGPT)	$\leq 2.5 \times$ ULN OR $\leq 5 \times$ ULN for participants with liver metastases
Albumin	$\geq 2.5 \text{ g/dL}$
Coagulation	
International Normalized Ratio (INR) or Prothrombin Time (PT)	$\leq 1.5 \times$ ULN unless participant is receiving anticoagulant therapy as long as PT or PTT is within therapeutic range of intended use of anticoagulants
Activated Partial Thromboplastin Time (aPTT)	$\leq 1.5 \times$ ULN unless participant is receiving anticoagulant therapy as long as PT or PTT is within therapeutic range of intended use of anticoagulants

^aCreatinine clearance should be calculated per institutional standard.

- 3.1.11 Female participants of childbearing potential must have a negative serum pregnancy within 72 hours prior to receiving the first dose of study medication. If the urine test is positive or cannot be confirmed as negative, a serum pregnancy test will be required.
- 3.1.12 Female participants of childbearing potential must be willing to use 2 methods of birth control or be surgically sterile, or abstain from heterosexual activity for the course of the study through 120 days after the last dose of study medication. Participants of childbearing potential are those who have not been surgically sterilized or have not been free from menses for > 1 year.

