6.1 Dose modifications for Pegylated Liposomal Doxorubicin

If patients experience treatment-related toxicities, their PLD dose should be reduced according to institutional prescribing and dose-reduction standards per the below tables.

If greater than two dose reductions are required, discussion and approval must be obtained by the Overall PI.

Recommended dose reductions for PLD (Doxil) per the FDA package insert:

Hand Foot Syndrome	
Toxicity	Dose Adjustment
Hand Foot Syndrome	
Grade 1: Mild erythema, swelling, or desquamation not interfering with daily activities	
• If no previous Grade 3 or 4 HFS, no dose adjustment.• If previous Grade 3 or 4 HFS, delay dose up to 2 weeks, then decrease dose by 25%.
Grade 2: Erythema, swelling, or desquamation interfering with, but not precluding normal physical activities; small blisters or ulcerations less than 2 cm. in diameter.	
• Delay dosing up to 2 weeks or until resolved to grade 0 or 1.• Discontinue doxil if no resolution after 2 weeks.• If resolved to grade 0 or 1 within 2 weeks: and no previous grade 3 or 4 HFS, continue treatment at previous dose or And previous Grade 3 or 4 toxicity; decrease dose by 25%
Grade 3: Blistering, ulceration, or swelling interfering	
• Delay dosing up to 2 weeks or until resolved to grade 0 or 1,

with walking or normal daily activities; cannot wear regular clothing.	
 then decrease dose by 25% • Discontinue doxil if no resolution after 2 weeks
Grade 4: Diffuse or local process causing infectious complications, or a bed ridden state or hospitalization.	
 • Delay dosing up to 2 weeks or until resolved to grade 0 or 1, then decrease dose by 25% • Discontinue doxil if no resolution after 2 weeks

Stomatitis

Toxicity	Dose Adjustment
Stomatitis	
Grade 1: Painless ulcers, erythema, or mild soreness	
 • If no previous Grade 3 or 4 toxicity, no dose adjustment. • If previous Grade 3 or 4 toxicity, delay dose up to 2 weeks, then decrease dose by 25%.

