Note: Permanently discontinue for any severe or Grade 3 drug-related AE that recurs or any life-threatening event.

¹ For patients with liver metastasis who begin treatment with Grade 2 AST or ALT, if AST or ALT increases by greater than or equal to 50% relative to baseline and lasts for at least 1 week then patients should be discontinued.

² Patients with intolerable or persistent Grade 2 drug-related AE may hold study medication at physician discretion. Permanently discontinue study drug for persistent Grade 2 adverse reactions for which treatment with study drug has been held, that do not recover to Grade 0-1 within 12 weeks of the last dose.

After discussion and approval from the Overall PI, dosing interruptions are permitted in the case

of medical / surgical events or logistical reasons not related to study therapy (e.g., elective surgery, unrelated medical events, patient vacation, and/or holidays). The reason for interruption should be documented in the patient's study record.

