Pembrolizumab Event of Clinical Interest Guidance Document

Each of the events above is described within this guidance document, along with site requirements for reporting these events to the Sponsor. The information collected should be entered into the narrative field(s) of the Adverse Event module in the database (please note, if narrative entry into the database is not available, please use the narrative text box on the 1727/AER Form). If additional Medical History or Concomitant Medications are reported, the Medical History and Concomitant Medication modules in the database must be updated.

In addition, the guidelines include recommendations on the management of these ECIs. These guidelines are intended to be applied when the physician determines the events to be related to pembrolizumab. Note: if after the evaluation the event is determined not to be related, the physician is instructed to follow the ECI reporting guidance but does not need to follow the treatment guidance (below). Therefore, these recommendations should be seen as guidelines and the treating physician should exercise individual clinical judgment based on the patient. For any question of dose modification or other treatment options, the specific language in the protocol should be followed. Any questions pertaining to the collection of this information or management of ECIs should be directed to your local Sponsor contact.

Dose Modification/Discontinuation

The treatment guidance provides specific direction when to hold and/or discontinue pembrolizumab for each immune related adverse event. Of note, when the guidance states to “discontinue” pembrolizumab this is the permanent discontinuation of treatment with pembrolizumab. “Hold” means to stop treating with pembrolizumab but resumption of treatment may be considered assuming the patient meets the criteria for resumption of treatment.

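### Section 5.2.2 omits two entry alternatives from Table 1, so a patient accepted on either one is barred from PLD from Cycle 2 with unchanged laboratory values

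*Combined protocol and SAP*

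**What the plan says.** **Entry.** Table 1 in Section 3.1.10 sets AST and ALT at 2.5 x ULN or less, with an alternative of up to 5 x "ULN for participants with liver metastases". It sets serum creatinine at 1.5 x ULN or less, with an alternative of measured or calculated clearance of at least 60 mL/min "for participant with creatinine levels" above that limit.

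**First dose.** Section 5.2.1: "Participants must continue to meet all eligibility criteria prior to dosing on Cycle 1, Day 1". The dose is 40 mg/m² (Section 5.3.1.2), and the protocol text sets no lower starting dose for raised liver values.

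**Later PLD doses.** Section 5.2.2: "Subsequent Cycles, on PLD treatment days: Patients must have all of the following". The list gives ANC, hemoglobin, platelets, creatinine (1.5 x ULN or less), liver function tests (2.5 x ULN or less) and ECOG status. The Nursing Protocol Education Sheet sends staff to this section for the subsequent-cycle criteria.

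**Neighbouring rules.**
- Table 2 footnote, Section 5.1: "The drugs may be held independent of one another, however, the study clock will not stop".
- Section 6.1: "If patients experience treatment-related toxicities, their PLD dose should be reduced according to institutional prescribing and dose-reduction standards". Its tables cover hand-foot syndrome, stomatitis, and neutropenia with thrombocytopenia. None is hepatic or renal.
- Table 3, footnote 1 (Section 6.2) opens "For patients with liver metastasis who begin treatment with Grade 2 AST or ALT" and sets a baseline-relative rule for stopping pembrolizumab.
- Appendix B, Overview, on managing events of clinical interest: "These guidelines are intended to be applied when the physician determines the events to be related to pembrolizumab".

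**The concern.** The entry criteria and the PLD re-treatment criteria treat the same value differently, and nothing has to happen to the patient for the answer to change. A woman with liver metastases and AST at 4 x ULN is eligible and receives full-dose PLD. At Cycle 2, with AST still at 4 x ULN, she does not meet the list. The same holds for a woman who entered on the clearance alternative and whose creatinine has not changed.

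The trial tests a combination. Because the two drugs can be held separately while the cycle clock runs, such a patient could move to pembrolizumab alone after one PLD dose, without toxicity or worsening. What is at stake is who actually receives the combination.

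**Working it through.** **1. The plan's own figures.** Inputs from Sections 13.2 and 13.4: n = 26, reject at 10 or more, null 25%, target 50%.
- Alpha = P(X ≥ 10), X ~ Bin(26, 0.25) = 0.0909; the plan states 0.091.
- Power = P(X ≥ 10), X ~ Bin(26, 0.50) = 0.916; the plan states at least 90%.

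Both reproduce. Section 5.2.2 enters neither calculation.

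**2. The two gates applied to unchanged AST/ALT, with liver metastases.** The fall needed to pass is 1 − 2.5/baseline.

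| AST/ALT (x ULN) | Cycle 1 Day 1 (limit 5) | PLD from Cycle 2 (limit 2.5) | Fall needed |
|---|---|---|---|
| 2.0 | pass | pass | none |
| 2.5 | pass | pass | none |
| 2.6 | pass | fail | 1 − 2.5/2.6 = 3.8% |
| 3.0 | pass | fail | 1 − 2.5/3.0 = 16.7% |
| 4.0 | pass | fail | 1 − 2.5/4.0 = 37.5% |
| 5.0 | pass | fail | 1 − 2.5/5.0 = 50% |

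Every stable value above 2.5 and up to 5 x ULN passes once and then fails. This takes the undefined liver-function entry in 5.2.2 to include AST and ALT, which is its ordinary meaning.

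**3. Creatinine.** With creatinine above 1.5 x ULN and clearance of at least 60 mL/min, Table 1 is met and 5.2.2 is not. This group is probably very small.

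**4. Does other text resolve it?**
- Section 6.1 is about treatment-related toxicity; an unchanged entry value is not one.
- Table 3 footnote 1 shows that raised entry values were foreseen, but it governs pembrolizumab only.
- Section 5.6 covers pembrolizumab alone after removal from PLD for PLD toxicity, which this is not.
- No maximum PLD hold is given for AST/ALT or creatinine.

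**5. PLD exposure by week 24 (day 168).**
- PLD days 1 + 28i: 1, 29, 57, 85, 113, 141, so 6 doses.
- Pembrolizumab days 1 + 21i: 1, 22, 43, 64, 85, 106, 127, 148, so 8 doses.
- PLD doses if the gate reopens at Cycle c = 1 + (6 − c + 1): 5 for Cycle 3, 4 for Cycle 4, 3 for Cycle 5, 2 for Cycle 6. If it never reopens, 1.

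**6. Lead-in.** Section 5.4 counts dose-limiting toxicity in Cycle 1, before 5.2.2 applies. The lead-in rule is untouched.

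**The case against.** **The stricter gate may be deliberate.** Entry and re-treatment limits need not match, 5.2.2 is written for PLD days, and Section 2.2 lists liver impairment among PLD toxicities. Giving the liver-metastasis rule in Table 3 for pembrolizumab alone fits that reading. It remains possible. Against it, the 5.2.2 list repeats the main Table 1 limits for ANC, hemoglobin, platelets, creatinine and AST/ALT and leaves out the alternatives for creatinine and AST/ALT, which looks more like shorthand than a decision. The plan does not say which.

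**The package insert may deal with it.** Several sections refer to it for PLD. It is not among the documents, so this cannot be checked. Section 5.2.2 is nonetheless an explicit protocol requirement.

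**Pembrolizumab alone is already provided for.** This stands. The Table 2 footnote permits separate holds, and footnote f to the Section 10 calendar foresees visits with pembrolizumab alone. A reader might infer that the patient's pembrolizumab is left in doubt during a PLD hold; it is not.

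**The effect on the trial is small.** This also stands. A reader might infer that power drops below the planned 90%. Assuming one affected patient with a benefit rate of 10% to 40% would give 89.1% to 91.0%, but the documents supply neither the number of such patients nor their benefit rate. Patients with liver metastases and raised transaminases may have less than a 50% chance of benefit whatever PLD they receive, so the loss could not be put down to the gate. Nor is the 1-of-6 case a lost endpoint: it needs the patient to stay on therapy without progression to week 24, which approximately meets the clinical benefit definition.

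**Footnote 1 of Table 3 is not a model for PLD.** A reader might want to borrow its 50% margin. It is a rule for stopping pembrolizumab, and nothing in the documents supports dosing PLD after a rise of that size.

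**Conclusion.** The inconsistency is real, and the protocol text does not resolve it. A patient admitted and given full-dose PLD on either Table 1 alternative cannot meet 5.2.2 from Cycle 2 unless the value improves. For AST/ALT the required fall ranges from just above zero to 50%.

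Severity is minor. The group is limited to patients with liver metastases and AST/ALT above 2.5 and up to 5 x ULN, plus those on the clearance alternative. The documents do not give its size; that it is small is a judgment. Sample size, alpha, the decision rule and the lead-in do not change, and no power loss can be derived. The conclusion rests on two readings: that the liver-function entry includes AST and ALT, and that failing a mandatory list means PLD is not given.

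**What to change.** In Section 5.2.2, replace the liver and creatinine lines with:

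- AST and ALT ≤ 2.5 x ULN; or, only for patients with liver metastases who entered above 2.5 x ULN, no higher than the baseline value and never above 5 x ULN.
- Serum creatinine ≤ 1.5 x ULN; or creatinine clearance ≥ 60 mL/min, only for patients who entered on that criterion.

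Do not allow a rise of up to 50% from baseline.

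**Cost.** Two lines of text and no new tests: AST, ALT and creatinine are in the serum chemistry already drawn on treatment days (Section 10, footnotes a and f). The downside is a slightly looser PLD re-treatment gate for a drug with listed liver toxicity. It is limited to values the plan already accepted for the first dose, and patients who entered within the main limits keep the present gate. A patient whose AST/ALT is above both 2.5 x ULN and her own baseline would still not receive PLD that day.
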